13.3 Analysis of Electrocardiograms

All ECG results will be listed on a by-subject basis. ECG parameters consist of heart rate (beats /min)), PR interval (msec), RR interval (msec), QRS Interval (msec), QT interval (msec), and QTcF interval (msec). Individual ECG values (parameters) will be listed by subject and visit. Baseline measurement is defined as the last available measurement prior to dosing. Post-baseline timepoints will be derived as per rules included in [Section 10.3](#).

For the safety population the following summary tables will be generated for the ECG data:

- Summary statistics (n, mean, standard deviation, median, minimum, and maximum) of the baseline value, the value at each post-baseline timepoint and the corresponding change from baseline for each continuous ECG parameter,
- Count and percentage of subjects with QTcF absolute value > 450 msec, >480 msec, >500 msec, <360 msec, <340 msec, <320 msec, and <300 msec at each post-baseline timepoint,
- Count and percentage of subjects with a mean change from baseline in QTcF intervals >30 msec, >60 msec >90 msec, <30 msec, <60 msec, and <90 msec at each post-baseline timepoint,
- Count and percentage of subjects with absolute heart rate > 100 bpm at each post-baseline timepoint,
- Count and percentage of subjects with heart rate change from baseline >10 bpm, >20 bpm, and >30 bpm at each post-baseline timepoint,
- ECG overall interpretation shift table from baseline to each post-baseline timepoint based on normal / abnormal categories.
- List of abnormal ECG results by safety evaluable subgroups.

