4 INTRODUCTION

This statistical analysis plan (SAP) describes the statistical methodology to be used for the reporting and statistical analysis of safety and pharmacokinetic (PK) clinical data as collected under SK Life Science clinical study protocol YKP3089C021 (amendment 4, 28 July 2017).

All statistical methods in this SAP are in regulatory compliance with the specifications as detailed in the International Conference on Harmonization (ICH) Guidelines:

- E3: Structure and Content of Clinical Study Reports;
- E6: Guideline for Good Clinical Practice; and
- E9: Statistical Principles for Clinical Trials.

Table, listing and figure templates (TLFs) for this study are presented in separate TLF documents.

All analyses described, statistical populations and TLFs programmed mentioned in this SAP are to be included in sections 14 and 16 of the clinical study report (CSR). All computer outputs detailing the statistical computations are to appear in an appendix: Statistical Documentation in the CSR as specified in the ICH E3 Guidance.

The signatures on this statistical analysis plan indicate approval of the safety and PK statistical analyses as detailed in each section of this SAP. These sections are agreed upon by SK Life Science (the Sponsor) and QDS (the Vendor).

This SAP may be revised at the end of the clinical investigation and prior to database lock to reflect specific details regarding protocol deviations and/or other data analysis clarifications (if needed).

This SAP supersedes any statistical considerations which were identified in the study protocol. Substantial differences from the study protocol are identified in this plan. If additional analyses are required to supplement the planned analyses then they will be performed and identified in the appropriate section of the CSR.

Computer program validation methods are to be agreed upon by the Sponsor and Vendor. Quality Control (QC) of all statistical components including derived SAS analysis datasets and TLFs will be performed by the Vendor prior to delivery to the Sponsor. All computational methods will be checked for accuracy. All “SAS

Notes generated from the computers programs will be checked for appropriateness.

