10 STATISTICAL METHODS

10.1 General Methods

Summary statistics and analyses will be presented by overall (YKP3089) and by safety evaluable subgroups. Categorical variables will be summarized using counts and percentages. Descriptive statistics for continuous variables will include mean, standard deviation, median, minimum, and maximum values. No inferential analysis will be performed.

SAS® version 9.4 or later will be used for all statistical analyses.

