The following conventions will be used for the derived visits with respect to safety variables:

1. If more than one actual visit date (including the unscheduled visits) falls within the same window, the visit closest to the target study day will be considered for analysis.
2. If 2 actual visit dates within a window are at the same distance from the target study day, the later visit with non-missing data will be considered for analysis. If repeated measurements are all taken on the same day, then the last measurement will be used.
3. Values recorded at Termination Visit will be mapped to the derived visit based on the window where the actual visit date falls in per rules 1 and 2 above.
4. Given the rules for completing the Termination Visit on eCRF (as defined in Protocol Section 9.1.14), the results recorded at Termination Visit will be summarized in the safety tables at both derived visit based on rule 3 above and at Termination Visit.

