10.4 Baseline Value and Change from Baseline

For all safety variables that involve eCRF data collected during study visits prior to the first dose of study drug, the baseline value is defined as the last non-missing value obtained immediately prior to the first dose.

Change from baseline variables will be calculated by subtracting the baseline value from the post-baseline derived visit (i.e., for derived Visit 3 to Visit 15 as per table in [Section 11.4](#)) for each subject.

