11.4.2 Phenytoin and Phenobarbital Dosing during Titration Phase

A by-subject data listing including phenytoin and phenobarbital dosing starting with baseline records up to an including end of titration (Visit 9) or early discontinuation for subjects who discontinue before Visit 9 will be prepared

separately for the two safety evaluable subgroups: subjects taking phenytoin and YKP3089, subjects taking phenobarbital and YKP3089, respectively.

Daily dose of phenytoin/phenobarbital will be computed using frequency and dose as recorded on eCRF: total daily dose (mg) = dose (mg) x frequency.

At each visit post-baseline during titration phase (ie, for visits up to and including Visit 9) change in phenytoin/phenobarbital total daily dose will be assessed for each subject based on comparison to the daily dose at the previous visit. The following variables will be derived:

1. Change from previous visit total daily dose of phenytoin/phenobarbital = total daily dose at current visit – total daily dose at the previous visit.
2. Change in total daily dose of phenytoin/phenobarbital categories:
 - no change, if total daily dose at current visit – total daily dose at the previous visit = 0.0
 - increase, if total daily dose at current visit – total daily dose at the previous visit > 0.0
 - decrease, if total daily dose at current visit – total daily dose at the previous visit < 0.0
3. Change from baseline total daily dose of phenytoin/phenobarbital = total daily dose at current visit – total daily dose at baseline.
4. Percent change from previous visit total daily dose of phenytoin/phenobarbital = [(total daily dose at current visit – total daily dose at the previous visit)/(total daily dose at the previous visit)] x 100. Note: percent change will have negative values if the change represents a decrease, positive values if the change represents an increase and will be 0% if there is no change.
5. Percent change from baseline total daily dose of phenytoin/phenobarbital = [(total daily dose at current visit – total daily dose at the baseline)/(total daily dose at the baseline)] x 100. Note: percent change will have negative values if the change represents a decrease, positive values if the change represents an increase and will be 0% if there is no change

Using baseline and end of titration phase total daily dose phenytoin/phenobarbital, the following variables will be derived:

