- a. After 12 months of participation in the open-label extension phase, subjects will be re-evaluated. Those who are benefiting from treatment with YKP3089 may continue use of the drug at the discretion of the investigator, until development is stopped by SK Life Science Inc, or the product is approved for marketing, or anytime at the discretion of SK Life Science Inc.
- b. Vital signs include blood pressure, heart rate (supine for 5 minutes), temperature, and respiratory rate.
- c. Height measured only at Visit 1.
- d. Brief neurological exam should be done only if symptoms require
- e. Administer the Baseline/Screening version of the C-SSRS at Screening. Administer the Since Last Visit version at all subsequent visits.
- f. 12-lead ECG will be performed once. Additional ECGs should be performed at any other time if clinically indicated.

- g. For female subjects of childbearing potential: If pregnancy is suspected at any time during the study, an interim test may be performed in addition to scheduled assessment.
- h. Laboratory assessment: Safety assessment includes blood chemistry and hematology. If the subject meets an exclusion criterion at Visit 1, an unscheduled laboratory sampling can be repeated for confirmation.
- i. Two blood samples will be collected for the determination of YKP3089 plasma levels: For patients that are taking YKP3089 in the morning and coming into the visits in the morning, the first blood draw will be collected upon subjects' arrival to the study unit; the second blood draw should be collected within 30 minutes to 2 hours after the medication is taken. Collect at visit 8 and/ or 9 depending on stability of dosing (doses must be stable for 2 weeks prior to these visits) of all concomitant AEDs including oxcarbazepine, topiramate, lamotrigine, lacosamide, clobazam, perampanel, levetiracetam, phenytoin and phenobarbital and YKP3089. YKP3089 PK draw is applicable for subjects on phenytoin and phenobarbital globally and all subjects at US sites.

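### The lower QTcF change cut-offs (<30, <60, <90 msec) carry no minus sign, so as printed they do not count QTcF decreases

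*SAP*

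**What the plan says.** The ECG section of the SAP (13.3) lists the QTcF summaries. One bullet counts subjects by change from baseline: "mean change from baseline in QTcF intervals >30 msec, >60 msec >90 msec, <30 msec, <60 msec, and <90 msec at each post-baseline timepoint". The bullet before it counts subjects by absolute QTcF. It has three high limits starting at 450 msec, and its list ends ">500 msec, <360 msec, <340 msec, <320 msec, and <300 msec at each post-baseline timepoint".

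The sign of a change is fixed in SAP 10.4: "Change from baseline variables will be calculated by subtracting the baseline value from the post-baseline derived visit". SAP 11.4.2 follows the same convention for phenytoin and phenobarbital dose, where "percent change will have negative values if the change represents a decrease". Nothing in 13.3, or in the list of changes from the protocol (SAP 16), says that the lower QTcF cut-offs refer to decreases.

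Two rules bear on the word mean. Under the scheduled assessments (SAP Appendix 1, footnote f), "12-lead ECG will be performed once". Under the windowing rules (SAP 10.3, rule 2), "If repeated measurements are all taken on the same day, then the last measurement will be used".

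**The concern.** The six change cut-offs are symmetric (30, 60 and 90 msec on each side) and follow a bullet with four low-side absolute limits. The heart-rate change bullet in the same section has upper cut-offs only. The < set for QTcF therefore looks deliberate, and the evident purpose is to count subjects whose QTcF shortened by more than 30, 60 or 90 msec.

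With a signed change and positive cut-offs, the rows do something else. A subject with no change, or with a small rise, meets all three < criteria, exactly as a subject with a large fall does. A rise of 45 msec falls in >30 and also in <60 and <90. A reader who takes the rows as counts of shortening would see nearly the whole population in them. A reader who takes them literally learns nothing beyond the > rows. In a study where "No inferential analysis will be performed", the descriptive tables are the safety result, so a row that cannot show what it was meant to show is a real, if small, loss.

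**Working it through.** The plan gives no figure to reproduce here, so the check is logical.

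**Inputs.** Change d = post-baseline minus baseline (SAP 10.4). Cut-offs c = 30, 60 and 90 msec, on both sides and without a minus sign (SAP 13.3). Lowest-severity absolute limit on the low side: 360 msec (SAP 13.3).

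**Identity.** Among the N subjects with a non-missing change at a timepoint, N(d < c) = N - N(d > c) - N(d = c). Apart from exact ties, each < row is the complement of its > row, whatever the distribution of QTcF.

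**Worked example (invented values).** Case A has QTcF going from 420 to 370, 400 to 405 and 400 to 435, that is d = -50, +5 and +35. Case B is the same except that the first subject stays at 420, that is d = 0, +5 and +35.

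| Row | Case A | Case B |
|---|---|---|
| >30 / >60 / >90 | 1 / 0 / 0 | 1 / 0 / 0 |
| <30 / <60 / <90 (as printed) | 2 / 3 / 3 | 2 / 3 / 3 |
| < -30 / < -60 / < -90 | 1 / 0 / 0 | 0 / 0 / 0 |
| absolute QTcF <360 | 0 | 0 |

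The six printed counts are identical although one subject lost 50 msec in case A. Only the rows with minus signs separate the two cases.

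**Does the absolute <360 row fill the gap?** A fall of size f from baseline b ends at or above 360 when f ≤ b - 360. A fall of more than 30 msec can therefore be missed when b > 390:

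- b = 400: falls above 30 and up to 40 msec are missed
- b = 420: falls above 30 and up to 60 msec are missed
- b = 440: falls above 30 and up to 80 msec are missed

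For b of 390 or less there is no gap, because every fall of more than 30 msec ends below 360. The absolute row also counts subjects who were already below 360 at baseline.

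**Illustration under an assumed distribution.** The documents give no mean or SD for QTcF change. Taking change as normal with mean -10, -5 or 0 and SD 15, 20 or 25 msec, the printed <30 row would hold about 88% to 99.6% of subjects, while about 2.3% to 21.2% would lie below -30. Two of these settings show the problem directly. Mean -10 with SD 20 and mean 0 with SD 15 both give 97.72% in the printed <30 row, since (30 + 10)/20 = 30/15 = 2. The share below -30 is 15.9% in the first and 2.3% in the second.

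**The word mean.** One ECG is scheduled per visit, same-day repeats resolve to the last value, and the row counts subjects at each timepoint. There is nothing to average.

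**The case against.** The strongest reply is that this is a typing slip with an obvious intended meaning, so it will do no harm. The table shells are elsewhere (SAP 4: "Table, listing and figure templates (TLFs) for this study are presented in separate TLF documents") and may carry the right signs. A row holding almost every subject would also be conspicuous at quality control. The symmetry does make the intention plain. But SAP 15.2 validates output by independent programming and by checking its format against the SAP, and two programmers who follow the printed text would agree with each other. A catch is possible but not assured.

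A second reply is that a minus sign may have been lost when the PDF was read. That cannot be fully excluded. A minus sign does survive in the screening day of the flowchart in SAP Appendix 1, but one surviving sign does not prove that none was lost elsewhere. The source should be checked first.

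A third reply is that the impact is small. This largely stands. The same section gives the minimum signed change at each timepoint, four low absolute-value counts and by-subject listings. Scheduled ECGs are few: screening, Visit 14 or termination, and yearly thereafter. Every fall of more than 60 msec from a baseline of 420 or less, and of more than 90 msec from 450 or less, ends below 360 and so enters the absolute row. Even so, a minimum shows one subject rather than how many, and the absolute row mixes falls with low baselines.

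The point about the word mean is editorial and changes no count.

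**Conclusion.** The point holds for the SAP as printed. Read with the SAP's own definition of change, the three lower QTcF rows carry no information beyond the upper ones, and no table counts subjects by size of decrease. This follows from an identity and needs no distributional assumption.

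The size is modest: three descriptive rows at a few timepoints, with shortening partly visible elsewhere. The number of subjects affected is unknown because the documents give no QTcF distribution; the percentages above are illustrative only. The conclusion assumes that the printed text matches the source and that the table would be programmed from it. It should be corrected because the rule gives an uninformative result if followed and the correction is almost free.

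**What to change.** Check the source PDF and the ECG table shell for the same signs. Then reword the bullet in SAP 13.3 as a count and percentage of subjects with change from baseline in QTcF >30, >60, >90, < -30, < -60 and < -90 msec, and delete the word mean. If the shell lacks the signs, change it in the same way.

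The cost is three minus signs and one deleted word. No data, table or analysis is added, and SAP 4 allows clarifications of this kind before database lock.

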13.4 Analysis of Vital Signs

All vital signs will be listed by-subject. Baseline measurement is defined as the last available measurement prior to the first dose. Post-baseline timepoints will be derived as per rules included in [Section 10.3](#). For the safety population the following summary tables will be generated for vital signs by safety evaluable subgroups and overall for the safety population:

- Summary statistics (n, mean, standard deviation, median, minimum, and maximum) of the baseline value, the observed value at each post-baseline timepoint and the corresponding change from baseline.
- Number and percentage of subjects with at least one post-baseline (scheduled or unscheduled) vital sign measurement meeting any of these criteria:

- Systolic Blood Pressure: <90 mmHg, >140 mmHg, >160 mmHg
- Diastolic Blood Pressure: <50 mmHg, >90 mmHg, >100 mmHg
- Pulse Rate: <60 bpm, >100 bpm
- Body Weight: decrease of $\geq 7\%$ from baseline and increase of $\geq 7\%$ from baseline
- Respiratory rate: <12 breaths/min, > 20 breaths/min
- Temperature: >38.0 °C, <36.0 °C

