13.2 Analysis of Clinical Laboratory parameters

Individual laboratory values (hematology, chemistry, and urinalysis) will be listed by subject and summarized using descriptive statistics (mean, standard deviation, median, minimum, and maximum) by safety evaluable subgroups and by visit. Both SI and Conventional units will be used in reporting summary results.

Baseline measurement is defined as the last available measurement prior to dosing.

Post-baseline timepoints will be derived as per rules included in [Section 10.3](#).

Individual change from baseline (the last available measurement prior to dosing) in laboratory values will be calculated and summarized descriptively (mean, standard deviation, median, minimum and maximum) for each post-baseline visit. Summary results will be presented by post-baseline timepoints.

Shift tables from baseline to each post-baseline timepoint will be prepared for all laboratory assessments based on the categories of Low, Normal, and High (for numerical results) or Abnormal and Normal (for categorical results).

Overall summary tables for shift from normal/abnormal (low or high) baseline to normal or abnormal post-baseline accounting for all post-baseline results during study will also be prepared. For these summary tables both scheduled and unscheduled post-baseline visits will be considered and subjects will be counted as shift to post-baseline normal if they do not have any abnormal (High or Low) post-baseline results during the treatment period; and as shift to post-baseline abnormal they have at least one post-baseline abnormal (High or Low) post-baseline results.

The following abnormality categories will be derived to evaluate liver function test results:

- AST
 - $\geq 3 \times \text{ULN}$
 - $> 5 \times \text{ULN}$
 - $> 10 \times \text{ULN}$
- ALT
 - $\geq 3 \times \text{ULN}$
 - $> 5 \times \text{ULN}$
 - $> 10 \times \text{ULN}$
- Total Bilirubin
 - $> 1 \times \text{ULN}$
 - $> 1.5 \times \text{ULN}$
 - $\geq 2 \times \text{ULN}$
- Alkaline phosphatase
 - $> 2 \times \text{ULN}$
 - $> 3 \times \text{ULN}$

The number and percentage of subjects with clinical laboratory test values in each category for the laboratory tests listed above will be summarized by each timepoint (including baseline) and overall (ie, anytime post-baseline), and by safety evaluable subgroups.

Pregnancy test results will be listed by subject (females only) by visit.

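### The vital-sign outlier table in SAP 13.4 takes no account of baseline, so it cannot separate values already past a limit from new ones

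*SAP*

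**What the plan says.** SAP 13.4 plans two vital-sign tables. The first gives summary statistics for the baseline value, the value at each post-baseline timepoint and the change from baseline. The second is the outlier table: "Number and percentage of subjects with at least one post-baseline (scheduled or unscheduled) vital sign measurement meeting any of these criteria". Its criteria are:

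- "Systolic Blood Pressure: <90 mmHg, >140 mmHg, >160 mmHg"
- "Diastolic Blood Pressure: <50 mmHg, >90 mmHg, >100 mmHg"
- "Pulse Rate: <60 bpm, >100 bpm"
- "Respiratory rate: <12 breaths/min, > 20 breaths/min"
- "Temperature: >38.0 °C, <36.0 °C"
- body weight, the one criterion defined as a percentage change from baseline

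Nothing in 13.4 limits the numerator or denominator by baseline status. No count past each limit at baseline is described, and no vital-sign shift table. SAP 16 lists the outlier table among the analyses that the SAP adds to the protocol, again with no baseline condition.

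Other SAP sections do show baseline status. In 13.2, laboratory tests have shift tables by timepoint and an overall shift that uses all post-baseline results, and the liver-test categories "will be summarized by each timepoint (including baseline) and overall". ECG interpretation (13.3), physical examination (13.5) and the C-SSRS (13.6) also have shift tables.

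**The concern.** A subject whose pulse is 56 before the first dose and stays there enters the table as a post-baseline low pulse. So does a subject whose pulse falls from 75 to 56 on treatment. The printed percentage treats them alike.

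In a randomised trial the control column would show how many subjects are flagged without the drug. Here every subject receives YKP3089, so only the subjects' own baseline can give that reference, and the table does not show it. A reader of the study report who sees a large percentage with low pulse or high systolic pressure may take it for an on-treatment finding, or may dismiss a real one as background. The table gives no means of deciding between the two.

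**Working it through.** **Reading the rule.** A subject is counted if any post-baseline value is past the limit. The counted group is therefore the sum of two groups: those past the limit at baseline and again later, and those not past it at baseline but past it later. SAP 13.4 reports only the sum.

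**Number of looks.** The SAP 10.3 windows for vital signs give 12 derived post-baseline visits in year 1 (Visits 3 to 14), 8 three-monthly visits to Day 1095, and Visit 15. That makes up to 12 + 8 + 1 = 21, plus unscheduled visits.

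**No figure to reproduce.** The SAP states no expected vital-sign rate, no sample-size calculation and no test. The documents give no means or SDs for vital signs, so what follows is an illustration on assumed values.

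**Model, no drug effect.** A subject's true level T is normal with mean m and between-subject SD b. Each reading is T plus independent normal error with SD w. Let p be the chance, given T, that one reading is past the limit, and let E be the average over subjects. With K post-baseline visits:

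- past at baseline = E[p]
- counted by SAP 13.4 = E[1 − (1 − p)^K]
- counted and already past at baseline = E[p × (1 − (1 − p)^K)]
- new onset among the rest = (counted − both) / (1 − past at baseline)

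Hand check of the first line: for pulse with m = 72, b = 8, w = 5, the total SD is √(64 + 25) = 9.43. Then (60 − 72)/9.43 = −1.27, which gives 10.2% below 60.

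**Results for K = 12** (numerical integration; ratios from unrounded values):

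| Assumed (m; b/w) | Past at baseline | Counted | Both | Both ÷ counted | New onset among the rest |
|---|---|---|---|---|---|
| Pulse below 60 (72; 8/5) | 10.2% | 32.4% | 9.4% | 28.9% | 23.0/89.8 = 25.6% |
| Pulse below 60 (72; 9/7) | 14.6% | 47.4% | 13.5% | 28.5% | 33.9/85.4 = 39.7% |
| Systolic above 140 (122; 10/7) | 7.0% | 26.9% | 6.2% | 23.1% | 20.7/93.0 = 22.3% |
| Systolic above 140 (122; 13/8) | 11.9% | 35.8% | 11.1% | 31.0% | 24.7/88.1 = 28.1% |

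**Separating the two effects.** About 29% (pulse) and 23% to 31% (systolic) of the counted subjects were already past the limit. The other 69% to 77% were not, although the model contains no drug effect. They are flagged mainly because there are 12 chances. With K = 1 the same model gives new onset of about 6% and 9% for pulse and about 5% and 7% for systolic pressure, against 26% and 40%, and 22% and 28%, with K = 12. A baseline split therefore isolates the carried-over part and leaves the repeated-look part in place.

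**Sensitivity.** Wider assumptions were tried. For systolic pressure, m/b/w of 118/10/6, 122/12/8 and 126/14/8 give 12% to 47% counted, of whom 20% to 39% were past the limit at baseline. For pulse, 76/9/5, 72/9/6 and 70/9/6 give 20% to 49% counted, of whom 27% to 34% were past it. With 21 visits these shares become 17% to 36% and 24% to 31%.

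**The case against.** The strongest reply is that the outlier table is a descriptive supplement. SAP 10.1 plans no inference, and the first table in 13.4 already gives change from baseline at each timepoint. By-subject listings allow any flagged subject's baseline to be looked up. Table shells are kept in separate documents (SAP 4) that are not available here, so a baseline column may exist in them. The revision history for SAP version 5.0 shows that liver-test analyses were deliberately opened to all baseline values, so counting everyone is a considered choice. Restricting to subjects inside the limit at baseline would also lose those who worsen from an abnormal start.

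Much of this stands. It rules out several stronger readings that a reader might infer:

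- **That the Protocol 6.2.2 endpoint is not analysed.** That endpoint is change from baseline, and the first table in 13.4 reports it.
- **That a drug effect on vital signs cannot be seen at all.** The mean-change summaries bear on that. The limitation concerns the outlier table.
- **That carried-over values explain most of the count.** In the main illustration they explain less than a third.
- **That 13.3 has the same defect.** It does plan the "Count and percentage of subjects with absolute heart rate > 100 bpm at each post-baseline timepoint" without a baseline column, but per timepoint, not as an ever-count. It also plans categories of change from baseline for QTcF and heart rate.
- **That a minimum change in blood pressure or pulse must be added.** Neither document gives a blood-pressure or vital-sign pulse change for this table, so there is no basis here for choosing one.

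The reply does not answer the remaining point. Means, SDs and ranges do not show how many flagged subjects began past a limit, and reading listings by hand is impractical with at least 1,000 subjects to be exposed for 6 months. The liver-test precedent supports the request, because those all-subject counts are tabulated at baseline as well.

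**Conclusion.** The point holds as a limitation of one descriptive safety table. As written, the counts in SAP 13.4 for the absolute limits combine carried-over and new values. With no control arm and no baseline count or shift, the table cannot separate them. Body weight is not affected.

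Under the main assumptions (normal variation, no drug effect, 12 visits), about 29% of pulse-below-60 flags and 23% to 31% of systolic-above-140 flags would be carried over. These shares illustrate the mechanism and do not predict this trial's results, since every mean and SD is assumed. That the SAP text omits the baseline display needs no assumption.

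No test or sample size is touched. The change is a cheap improvement to how the table can be read, not the correction of an invalid analysis.

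**What to change.** In SAP 13.4, for each absolute limit on systolic and diastolic pressure, pulse, respiratory rate and temperature:

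1. Keep the planned all-subject count, so that subjects who worsen from an abnormal baseline stay visible.
2. Show beside it the number and percentage of subjects past the same limit at baseline, using the baseline already defined in 13.4.
3. Add a shift from baseline (past or not past the limit) to any post-baseline value (past or not past), using scheduled and unscheduled values as the overall laboratory shift in 13.2 does. Report from it the new-onset count, with subjects not past that limit at baseline as the denominator.
4. Add a footnote that the any-visit percentages, including new onset, rise with the number of visits and should not be read against a single baseline reading as a measure of drug effect.

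A baseline column for the absolute QTcF and heart-rate counts in 13.3 is optional, since change categories are planned there.

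The cost is SAP wording and table shells. All the values are already collected. The tables get longer and denominators differ by criterion, so each needs to be printed. The repeated-look effect remains.
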